9.3 Reporting Requirements

*Note: SAEs/UADEs are reported electronically via EDC. If the EDC system is not available, the paper SAE Back-up form should be used for reporting and EDC should be updated once available. The SAE Back-up form should be sent to Medpace Clinical Safety as follows:

Email: [contact] OR [contact] or [contact].

9.4 Device Failures and Malfunctions

All RMRS device failures and malfunctions related to the investigational aspects of the device (e.g. BgRT functionality) shall be reported within 24 hours after becoming aware to RefleXion Medical personnel via data entry to appropriate eCRFs. If EDC system is not available to report device malfunction, the appropriate paper CRF needs to be completed with the information and faxed to the RefleXion Medical personnel listed in the current Study contact list provided in the Study binder. Device failures and malfunctions should also be documented in subject's medical record.

Study-applicable device failures and malfunctions should be reported on the appropriate eCRF within 24 hours after becoming aware of event, however failures and malfunctions should not be reported as adverse events in and of themselves. In the event that device failure or malfunction cause an AE, the AE and specific event causing the AE should be reported on the appropriate eCRFs.

All RefleXion Medical non-study device failures or malfunctions should be reported to the RefleXion customer service organization.

9.5 Reporting to Regulatory Authorities, Institutional Review Boards and Investigators

RefleXion Medical will code and report all verbatim adverse events to study investigators and regulatory authorities, as applicable. RefleXion Medical or its designees will utilize Medical Dictionary for Regulatory Affairs (MedDRA) to code all AEs reported in the trial. RefleXion Medical will report any UADEs to FDA as per Medical Device Reporting guidelines (21 CFR 803).

The site Principal Investigator is responsible for informing the IRB of UADE, SAE and/or AEs per local requirements. A copy of this report should be provided to RefleXion Medical study personnel.

Adverse events and protocol deviations along with the sites they occurred will be identified by RefleXion Medical in applicable reports and correspondence with FDA.

10. RISK BENEFIT ANALYSIS

Engineering evaluation of the RMRS has demonstrated that the safety features of the RMRS have been shown to be effective through testing and that the overall residual risk is considered to be within the clinically acceptable level.

10.1 Study Risk Management Procedures

Eligibility criteria have been selected that exclude patients who are at a higher risk for experiencing an anticipated adverse event in order to reduce the risks to patients who participate in this study.

Study subjects will continue to receive standard of care treatments throughout the study, which are not part of study procedures. The treating physician will counsel the subjects on the risk of the treatments including the risk of surgery, radiation therapy and any other treatment appropriate for their type and stage of cancer.

Monitoring will take place throughout the study and adverse events will be recorded in the Patient's charts and on Case Report Forms developed for the study. Investigational device training will be conducted at each initiated study center and appropriate training records will be maintained.

10.2 Known and Anticipated Risks

The study procedures may include multiple administrations of FDG. Reviews of the oncology and cardiology literature have not revealed known adverse reactions attributable to FDG administration aside from sporadic hypersensitivity reactions¹⁷. Even at multiple administrations, FDG is not expected to result in meaningful toxicity due to radioactivity exposure as each injection results in a total whole body dose of 20 mSV (2000 mrem) or less^{18,19}. Therefore, exposure from multiple administrations in the BgRT workflow is comparable to the annual federal limit for radiation workers (50 mSv; 5000 mrem) and is significantly below that experienced by patients undergoing radio-iodine therapy for thyroid disease (200 mSv; 20,000

mrem). In fact, the radiation exposure of the multiple FDG injections is considerably less than the incidental exposures experienced by patients during other routine aspects of current radiotherapy practice; for instance, cumulative radiation exposure originating from both daily image-guidance using cone beam computed tomography and from scatter dose during high-energy beam delivery meaningfully exceed the radiation exposure that can result from multiple FDG administrations. These observations are summarized in the following table:

	Approximate Effective Dose (mSv)
2-6 FDG injections (10-20 mCi each)	10-120
Conventional Radiotherapy: 30 CBCT Image-Guidance Procedures	Up to 1000
Conventional Radiotherapy: Scatter Dose from 60 Gy Prescription	120-200

 Table 3: Comparison of effective dose from multiple FDG administrations and other incidental radiation

 exposures from currently used procedures in conventional radiotherapy

This comparison of FDG dose versus incidental dose from routine aspects of current radiotherapy also holds true for individual organs. For example, the organ most at risk from FDG exposure, the bladder, receives approximately 6-12 cGy from each FDG injection (36-72 cGy in the case of 6 injections). This exposure is an order of magnitude below the incidental radiation that the bladder receives from a course of conventional prostate radiation, which can range from approximately 500 cGy to 8100 cGy, depending on the proximity of the portion of bladder being assessed to the prostate gland.

This argument for tolerability, which is based upon first principles of radiation safety, is further supported by empiric evidence from human and animal studies. Cox et al. conducted a phase I trial of very high doses of FDG to determine whether the radiation emitted by FDG could be utilized for therapeutic effect²⁰. In their study, three patients were given progressively higher doses of FDG (100 mCi/m², 150 mCi/m², and 200 mCi/m²) with a single injection. With a median follow-up of 6 months, no dose limiting toxicities were observed. Notably, the third patient in the study received 400 mCi of FDG. Multiple investigations have utilized serial weekly FDG PET scans over a 6 week course of fractionated radiotherapy to assess early tumor response during treatment; although toxicity was not a formal endpoint in these imaging studies, nonetheless no unexpected adverse events attributable to multiple administrations of the tracer were reported^{21,22}. Moadel et al. determined that the dose-limiting organ in human patients treated with high-dose FDG would be the red marrow using the Medical Internal Radionuclide Dosimetry Formalism, and further determined that the tolerance dose that would result in 5% risk of red marrow suppression at 5 years (TD 5/5) was 4760 mCi^{23,24}. In addition to these human investigations, a number of animal studies of very high FDG doses (up to 6 mCi per 20 g mouse) have, to date, not resulted in any observable toxicity²².

Although this evidence and first principles of radiotherapy safety provide reassurance that multiple FDG administrations at a diagnostic dose are unlikely to cause measurable toxicity, nonetheless this investigation seeks to provide additional evidence for the safety of multiple FDG administrations. Cohort II will seek to capture evidence regarding the tolerability of multiple FDG administrations through standard grading of toxicities during therapy. Study subjects will be observed for potential FDG administration related toxicity and AEs related to the organs at theoretical risk, which include the bladder and bone marrow. These adverse events may include anemia, thrombocytopenia, bleeding, lymphopenia, neutropenia, hematuria, bladder spasms, transient hypotension, hypo- or hyperglycemia and/or had transient increases in alkaline phosphatase.

Other potential FDG exposure related risks and mitigations include:

- Overexposure of bladder to FDG, mitigated by proper hydration prior to FDG (besides fasting) and frequent voiding for at least one hour after completion of the procedure
- Radiation exposure to nearby individuals, mitigated by limitation of exposure to others until the FDG decay is complete
- Risk of FDG overdose, mitigated by proper documentation of FDG administration and corresponding radiation exposure

In addition to FDG exposure risk, subjects will receive localization (positioning) scans with the RefleXion system integrated fan-beam kVCT imaging prior to each PET image collection session. The risks to the patient from this imaging procedure are expected to be in accordance with the general risks of low-dose radiation exposure, including the long-term risk of secondary malignancy.

11. STUDY COMMITTEES

11.1 Safety Monitoring Committee

A Safety Monitoring Committee (SMC) consisting of individuals with pertinent expertise (including but not limited to a non-site radiation oncologist, site radiation oncologist and/or physicist, RefleXion Medical physician and RefleXion Medical technical staff) will be formed. Responsibilities of the committee are outlined in the SMC charter and will include oversight of the overall conduct of the study with regard to study progress, ensuring subject safety and overall data quality and integrity. The SMC will be responsible for assessing Cohort I data to identify and confirm the RRFD in the context of the primary endpoint (achieving the minimum activity level in the treatment target area [BTZ]) according to the modified 3+3 design outlined in *Figure 5*. Additionally, the SMC will review Cohort I secondary analyses and has the discretion to consider the performance of the studied FDG dose in the context of secondary endpoints. If at the RRFD, the performance of emulated BgRT delivery meets statistical parameters for success in the primary endpoint and there are no objections arising from the other secondary analyses, then the SMC will open Cohort II to accrual. Additionally, the SMC will monitor patient safety by reviewing AEs and SAEs

including AE onset, intensity, action taken, and outcome on a regular basis for the duration of the study for both cohorts.

11.2 Independent Image Reviewers

Independent image reviewers with pertinent expertise in radiation oncology and/or radiology will assess RMRS PET and third-party diagnostic PET/CT images in order to determine the agreement standard and external image concordance secondary endpoints for Cohort I and Cohort II. All the readers will be trained using identical training data set and image review software programs as detailed in the image review charter (IRC). RMRS PET images will be read by three radiation oncologists and third-party diagnostic PET/CT images will be read by three radiologists. Readers will be blinded to patient diagnosis, reader evaluations, images from the compared device (i.e. the radiologist reviewers for the diagnostic PET/CT would be blinded to the patient's RMRS PET and RMRS kVCT for localization) but not the patient's Sim CT and other clinical data. Each reader will use the applicable schema and answer the same set of questions to generate a positive or negative decision as outlined in Section 6. Image assessments will be directly entered by the central reviewers in the dedicated imaging eCRF and signed electronically.

12. ETHICAL CONSIDERATIONS

12.1 Compliance with Good Clinical Practices (GCP)

The investigator is responsible for ensuring the study is conducted in accordance with clinical principles and practices originating from the Declaration of Helsinki. The study should be conducted in accordance to the Good Clinical Practices (GCP) and applicable local requirements, whichever provides subjects greater protection.

12.2 Institutional Review Board

A copy of the protocol, proposed ICF, other written subject information, including any proposed advertising material must be submitted to the IRB for written approval. A copy of the written IRB approval of the protocol and ICF must be received by RefleXion Medical before recruitment of subjects into the study.

The principal investigator is responsible for submitting and, where necessary, obtaining approval for all subsequent amendments to the protocol, and any changes to ICF, as well as obtaining annual IRB approval and renewal throughout the study. The principal investigator must also notify the IRB regarding protocol deviations, UADEs, SAEs occurring at the site and other UADE/SAE reports received form RefleXion Medical in accordance to the local requirements and procedures.

Copies of the investigator reports and all IRB approvals, including continuance of IRB approval, must be sent to RefleXion Medical.

12.3 Written Informed Consent Form

RefleXion Medical will provide the Study Informed Consent Form Template to the investigator to prepare for use at his/her site. The written Informed Consent documents should be prepared in the language(s) of the potential subject population.

RefleXion and the reviewing IRB must first approve the study ICF before use. The ICF must be in alignment with current guidelines as outlined by the GCP guidelines, Declaration of Helsinki and International Conference on Harmonization (ICH).

Prior to participating in the study, each subject must give written Informed Consent after the context has been fully explained to the subject in a language that is easily understood by the subject. The subject must be given enough time and opportunity to ask questions and have those questions answered to his/her satisfaction. Written Informed Consent process must be recorded appropriately by means of the subject's, or his/her legal representative's, dated signature. The consent process must be documented in the subject's medical chart.

12.4 Amending the Protocol

This protocol must be followed exactly and can be altered only by written amendments. Following appropriate approval, the revised protocol will be distributed to all participating sites. Each site must obtain IRB/EC approval before implementing the revised protocol.

12.5 Emergency Actions

RefleXion Medical accepts the rights of the Investigator to deviate from the protocol in an emergency when necessary to safeguard the life or the physical well-being of a study subject. The Investigator must give notice of any emergency deviations and justification for the deviation to RefleXion Medical and IRB as soon as possible after the deviation, in any event no later than 24 hours after the emergency.

12.6 Protocol Adherence

Prior to beginning of the study, the Investigator must sign the Investigator Agreement documenting his/her agreement to conduct the study in accordance with the protocol. The Investigator must not make any changes or deviate from this protocol, except to protect the life and physical well-being of a subject in an emergency. Each deviation from the protocol must be documented with the date and reason for the deviation and reported to RefleXion Medical as soon as possible, and to the IRB per local guidelines and regulations.

13. STATISTICAL CONSIDERATIONS

13.1 Sample Size Calculation

13.1.1 Cohort I: RRFD Cohort

This objective of Cohort I is to identify the Recommended RefleXion FDG Dose (RRFD). Dose levels of 15 and 20 mCi (if necessary) will be assessed sequentially in an escalation protocol. To that end, a modified 3+3 design will be utilized wherein meeting the activity level threshold, not dose-limiting toxicity, will be the relevant endpoint. The RRFD will be primarily based upon the lower FDG dose level where 5 to 6 out of 6 subjects have an Activity Concentration greater than 5 kBq/ml. As mentioned in section 4.2, dose escalation to the second dose level can also be triggered by secondary analysis of technical factors related to radiotherapy plan quality derived from the RMRS PET imaging data.

The modified 3+3 design with 6 patients at the 'Recommended RefleXion FDG Dose level' aims to ensure that the observed proportion of patients below activity threshold to be less than 33%. The following table shows the probability of observing at most 1 of 6 below activity threshold with various true below activity rates:

True below activity rate	40%	30%	20%	10%
Probability at most 1 of 6 patients below activity threshold	0.233	0.420	0.655	0.886

Probability of Observations at Most 1 of 6 below Activity Threshold

As such, either 6 patients will be accrued if 15 mCi FDG meets criteria or 9 or 12 total patients will be accrued if escalation to 20 mCi is required.

Descriptive statistics will be utilized for all secondary endpoints.

13.1.2 Cohort II: Emulated Delivery Cohort

The purpose of Cohort II is to emulate delivery of BgRT plans based upon clinical PET data obtained on the RefleXion system from human subjects using the RRFD established in Cohort I.

The primary endpoint is the percent of radiotherapy fractions where the emulated BgRT dose distribution *in silico* is shown to be consistent with the approved BgRT treatment plan (i.e., 95% of DVH_{Delivered} points for the BTZ and OARs fall within the bounded DVH of the approved BgRT plan).

As previously described in Section 4.3, a BgRT dose distribution is considered evaluable if:

• The subject has successfully undergone BgRT plan creation, physics quality assurance, and plan approval

• A "pass" signal is achieved at the PET PreScan evaluation preceding the long-duration PET emission collection

The sample size was determined a priori to represent a sufficient number of dose distributions for a robust sampling of BgRT deliveries under clinical conditions, including both before and after start of external beam radiotherapy. A sample size of 16 evaluable dose distributions from 8 to 22 subjects will be obtained to inform the concurrence between BgRT dose distributions and approved BgRT plan. Assuming the concurrence rate by the outcomes of primary endpoint follows a binomial distribution, the sample size achieves cumulative probability of approximately 0.81 that at most 1 inconsistency out of 16 evaluable dose distributions when true inconsistency rate is 5%, as shown in below table:

Cumulative Probability at most 1 inconsistency out of 16 evaluable distributions:

True inconsistency rate	40%	30%	20%	10%	5%
Probability at most 1 non- concurrence out of 16 assessments	0.003	0.026	0.141	0.515	0.811

Given that no prior data exists for biology-guided radiotherapy, we will report descriptive statistics for secondary endpoints, as defined in section 4. The summary statistics for BgRT workflow steps will be described for all enrolled patients including those with non-evaluable dose distributions.

13.2 General Consideration

Data collected will be presented using summary tables, patient data listings, and figures (TLFs). Continuous variables will be summarized using descriptive statistics with the mean (standard deviation), median, minimum, and maximum. Categorical variables will be summarized by frequencies and percentages. TLFs will be presented separately for each Cohort. Cohort I will be summarized by dose level, if more than 1, and total. Cohorts I and II will be summarized by site of disease (bone, lung) and total.

13.2.1 Patient Disposition

A summary of patient disposition including patients who enrolled in the study, patients who completed the study, terminated study early, and the reasons for early study termination

13.2.2 Demographics and Baseline Characteristics

The demographic characteristics (e.g., age, race, ethnicity, gender, baseline height, and baseline body weight) and baseline characteristics such as ECOG PS, disease status etc. will be summarized and listed. Categorical characteristics (e.g., gender, ethnicity and race, ECOG) will be summarized by frequency and percentage.

13.2.3 Prior and Concomitant Medications

Each medication will be coded to a preferred term and an Anatomic Therapeutic Classification (ATC) code using WHO Drug dictionary. Prior concomitant medication is defined as any medication ended prior to the first day of the FDG administration. The number and percentage of patients taking each prior or concomitant medication will be displayed by medication class, preferred term and treatment group.

13.2.4 Safety Analyses

Extent of FDG exposure will be summarized by number of doses, cumulative dose, any dose interruption and dose reduction. Safety will be assessed through AEs, changes in laboratory parameters, and vital signs. AEs will be coded using the Medical Dictionary for Regulatory Activities (MedDRA); AE severities will be graded using the CTCAE criteria.

All AE data will be listed. Notably, actual delivery of BgRT treatment to the patient is not part of this investigation. All treatment-emergent AEs (TEAEs), defined as adverse events not present prior to FDG exposure and study procedures, will be summarized, as follows:

- All TEAEs by worst Grade
- All TEAEs related to the study device and/or FDG exposure by worst Grade
- All Grade 3/4/5 TEAEs
- All Treatment Emergent SAEs by worst Grade
- All Related Treatment Emergent SAEs related to study device and/or FDG exposure by worst Grade

Observed and changes from baseline in laboratory values will be summarized. Laboratory values outside the corresponding normal ranges will be flagged in listings.

Observed and Changes from baseline vital signs and ECOG data will be summarized similarly as laboratory values.

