5. STUDY POPULATION

- 5.1 Selection Criteria
- 5.1.1 Inclusion Criteria
- 1. Age greater than 21 years
- 2. A new or prior diagnosis of biopsy-proven cancer with a solid tumor (non-hematologic, non-lymphoma)
- 3. At least one active tumor in the bone or lung which is either the primary tumor or metastatic lesion determined either by biopsy or imaging suspicious of active disease
- 4. Target tumor size ≥2cm and ≤5cm

- Target lesion in the bone or lung that is discrete and assessed by investigator to be FDG-avid (i.e. SUV_{max}≥6 on third-party diagnostic PET/CT performed within 60 days with no new intervening oncologic therapies)
- 6. ECOG Performance Status 0-3
- 7. Must have completed any other oncologic therapies at least 15 days prior to planned start of study procedures (preferably 30 days) and must have no plans to initiate systemic therapy until after study follow up is complete -OR- must be recorded by physician to have an active candidate lesion that is unresponsive to ongoing systemic therapy
- 8. Females of childbearing potential should have negative urine or serum pregnancy test within 14 days prior to initiation of study scans.
- 9. Demonstrate adequate organ function:
 - a. Absolute neutrophil count (ANC) > 1,500 /mcL
 - b. Platelets > 50,000 / mcL
 - c. Hemoglobin > 8 g/dL
 - d. No gross hematuria
- 10. For Cohort II only: Patient is dispositioned to undergo SBRT to a bone or lung tumor

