6. STUDY PROCEDURES

6.1 Written Informed Consent

Written Informed Consent must be obtained for all subjects who are screened and meet the general inclusion/exclusion criteria prior to enrollment.

The subject or the subject's Legally Authorized Representative (LAR) will be asked to sign the Informed Consent form before any study-specific tests or procedures are performed. The Informed Consent Form (ICF) must be approved by the study Institutional Review Board (IRB). Electronic informed consent procedures may be utilized if approved by the IRB and consistent with FDA guidance on use of electronic informed consent in clinical investigations. Study personnel should explain that even if a subject agrees to participate in the study and signs an Informed Consent Form, imaging or other tests may demonstrate that the subject is not a suitable candidate for study participation/treatment. All subjects that have signed

the ICF, met all study eligibility criteria (and none of the exclusion criteria), and present for the RefleXion Imaging-only session will be considered enrolled at the time of FDG administration.

A Screening and Enrollment Log will be maintained by the site to document basic information such as date screened and reason for screen failures for subjects who fail to meet the study eligibility criteria. Screenfailed subjects and their reason(s) for screen failure will be documented and may be entered into the electronic database, but they will not be followed beyond the screening visit, and no further data will be collected/recorded.

Investigator and/or study personnel at the site will review the study requirements with the subject to maximize compliance with the follow-up schedule. Study personnel will instruct subjects to return for study assessments per Study Event Schedule for the applicable cohort the patient is enrolled in.

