6.3.1 Baseline Visit

The following baseline data should be collected within two weeks prior to RMRS PET Imaging-only session for all subjects enrolled in Cohort II and documented in the case report form (CRF):

- Confirmation that all inclusion criteria and none of the exclusion criteria are met.
- Demographics, medical history and physical exam
- Complete Blood Count (CBC)
- Comprehensive Metabolic Panel (CMP)
- Blood glucose
- Urinalysis

RefleXion Medical Radiotherapy System RefleXion Medical Inc., Confidential

- ECOG performance status
- Baseline assessment of bladder and bone marrow with CTCAE grading
- Pregnancy test (required for women of child-bearing potential only, if applicable within 14 days prior to the initiation of the study scans.)

For patients undergoing systemic therapy at the time of enrollment, decisions regarding whether to continue the systemic therapy or undergo a wash-out will be made by the treating physician in accordance with standard of care for combining radiation and drug therapy.

Additionally, a Sim CT should be obtained within two weeks prior to the PET Imaging-only session if not already planned to be obtained as standard of care. Any additional institutional guidelines must be followed regarding negative pregnancy testing in patients about to undergo radiation therapy.

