Unanticipated Adverse Device Effect (UADE)	Any serious adverse effect on health or safety or any life- threatening problem or death caused by, or associated with a device, if that effect, problem, or death was not previously identified in nature, severity, or degree of incidence in the investigational plan or application (including a supplementary plan or application), or any other unanticipated serious problem associated with a device that relates to the rights, safety, or welfare of subjects.	21 CFR Part 812

Underlying diseases are not reported as Adverse Events (AEs) unless there is an increase in severity or frequency during the course of the study. Death is not an adverse event but should be reflected as an outcome to another specific AE. Any AE experienced by the study subject after enrollment whether during or subsequent to the study procedures must be collected and recorded in the (e)CRF.

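### The treatment-emergent definition in 13.2.4 has no worsening clause, so, read literally, all five adverse event summaries leave out an event present before FDG that rises in grade afterwards

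*Combined protocol and SAP*

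**What the plan says.** Section 13.2.4 defines treatment-emergent adverse events (TEAEs) as those "defined as adverse events not present prior to FDG exposure and study procedures". Five summaries follow: all TEAEs, related TEAEs, "All Grade 3/4/5 TEAEs", treatment-emergent serious events, and related treatment-emergent serious events. Every one carries the treatment-emergent restriction. The same section also lists all AE data, summarizes laboratory changes from baseline and flags out-of-range laboratory values in the listings.

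Section 9.1 sets the reporting rule: "Underlying diseases are not reported as Adverse Events (AEs) unless there is an increase in severity or frequency during the course of the study". It requires collection of AEs that occur after enrollment, and 6.1 fixes that moment: subjects "will be considered enrolled at the time of FDG administration". Section 9.2 takes signs and symptoms of progression of the existing disease out of the AE definition.

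For Cohort II, the baseline visit in 6.3.1 includes "Baseline assessment of bladder and bone marrow with CTCAE grading". Table 2 and Attachment 1 schedule an AE assessment at baseline in that cohort and repeat the directed bladder and marrow grading 72±24 hours after the last FDG injection.

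**The concern.** A TEAE definition usually has two parts: events that start after exposure, and events already present that get worse after it. Only the first part is here. The collection rule in 9.1 treats worsening as something to report, while the rule that decides what is counted in the tables does not mention it.

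This matters because Cohort II is meant to add evidence on the safety of repeated FDG injections. If worsening from an abnormal baseline is left out of the counts, the tables lean toward under-reporting. Two competent analysts working from the same data could also produce different tables, depending on how each reads the definition.

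**Working it through.** The point concerns a definition, so there is no figure to reproduce. The check sets the passages side by side.

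**1. Is there another definition?** No other section of the document defines treatment-emergent or adds a worsening clause. Section 13.3 says a SAP will be finalized before database lock, but no text in hand supplies the missing clause.

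**2. Trace one case.** Take a hypothetical finding at Grade 1 before FDG that reaches Grade 3 afterwards.

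| Summary in 13.2.4 | As written | With a worsening clause |
|---|---|---|
| All TEAEs | out | in |
| Related TEAEs | out | in if judged related |
| Grade 3 and above | out | in |
| Serious TEAEs | out | in if serious |
| Serious and related | out | in if both |

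Read literally, the case enters 0 of 5 tables, including the one for severe events.

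**3. Compare with 9.1.** If the finding belongs to an underlying disease, its increase in severity makes it a reportable AE. It is therefore collected and listed, yet not counted in any AE summary. Findings that are signs of cancer progression are outside this comparison, because 9.2 does not treat them as AEs.

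**4. Is the case foreseeable?** In Cohort II it is.

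- The inclusion criteria in 5.1.1 require only "Hemoglobin > 8 g/dL" and platelets above 50,000/mcL, exclude gross but not microscopic blood in the urine ("No gross hematuria"), and allow ongoing systemic therapy in some subjects.
- Section 10.2 names the same organ systems as the ones to watch: "These adverse events may include anemia, thrombocytopenia, bleeding, lymphopenia, neutropenia, hematuria, bladder spasms".
- Bladder and marrow are graded before FDG, so a pre-FDG grade is on record.

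One assumption enters here: that values near the eligibility floors would carry a CTCAE grade. The documents do not reproduce the CTCAE cut-points.

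**5. Where else would the worsening show?** It would appear in the AE listing and, for a laboratory value, in the change-from-baseline summary. Section 13.2 summarizes continuous variables by mean, standard deviation, median and range, which does not count subjects whose grade rose. A non-laboratory event such as bladder spasm would appear in no 13.2.4 summary, only in the listing.

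**6. Size.** The documents give no frequency of baseline findings, so the number of omitted events cannot be estimated. For scale only, one subject in the Cohort II total is 1/8 = 12.5% at the planned minimum and 1/22 = 4.5% at the maximum. That is the weight of any single subject, not an estimate of this effect.

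**The case against.** The strongest reply is that 13.2.4 speaks of adverse events, not conditions, that were absent before FDG. Under 9.1 an underlying disease is not an AE until it worsens, and collection starts at enrollment, which 6.1 places at FDG administration. On that reading the worsening is the AE, it was not present before FDG, and 9.1 and 13.2.4 agree.

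This reading is possible, and it means the mismatch with 9.1 exists only on the literal reading; the two sections do not flatly contradict each other. But 13.2.4 neither states it nor cites 9.1, and the 9.1 sentence concerns underlying diseases and whether to report them, not how to tabulate. It also fits Cohort II poorly, where AEs and directed toxicity grades are recorded before FDG. Graded events therefore do exist before exposure in that cohort.

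Other replies stand as limits. No data are lost, and with at most 34 planned subjects (12 + 22) the listings can be read in full. Laboratory worsening in Cohort II is partly covered by the change-from-baseline summaries. The SAP is still to come and could settle the wording.

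Two stronger inferences are tempting. A reader might infer that the bladder and marrow toxicity rates of Cohort II secondary endpoint 4 will be understated. The documents do not support this: 3.2.2 and 4.3 do not tie that endpoint to TEAEs, and 13.2.5 handles secondary endpoints separately. A reader might also carry the laboratory examples over to Cohort I. That is unsupported too, because Table 1 and Attachment 1 schedule blood counts and urinalysis at baseline only in that cohort, and the baseline AE assessment is marked for Cohort II.

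**Conclusion.** Wrong as written (minor). The stated rule, applied literally, leaves worsening of a pre-FDG event out of all five AE summaries, and nothing elsewhere corrects it. The direction is toward under-reporting and the size is unknown. The effect is confined to descriptive safety tables; no test, sample size, primary endpoint or decision rule is touched.

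The conclusion rests on two things: that an analyst would follow 13.2.4 as worded, and that some Cohort II subjects enter with gradable findings that are not signs of progression. The pre-FDG grading and the eligibility limits make the second plausible, but the documents do not quantify it.

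**What to change.** In 13.2.4 keep the present definition and its anchor, and append a clause: or present before and increasing in CTCAE grade or frequency afterwards. Add a cross-reference to 9.1, and carry the same wording into the SAP before it is finalized.

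Optionally, for Cohort II, tabulate the shift from the directed baseline bladder and bone marrow grade to the directed grade at 72±24 hours after the last FDG injection, giving the number of subjects whose grade rose. The table should use those two time points, because they are when the directed grading is done.

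The cost is one clause and, if wanted, one table, from data already collected. No procedure changes. The only downside is that reported TEAE rates may rise slightly.
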